### 6.4 STUDY TREATMENT COMPLIANCE

Participants will be instructed on proper instillation and storage of the study drug and provided with written instructions. To assess adherence to the protocol regarding administration of the study product, participants will be instructed to record in a dosing compliance diary on a daily basis. Dosing compliance will be assured by an in-office review of a dosing diary. [REDACTED]

[REDACTED] Participants will be reinstructed on dosing compliance and this will be documented in the source documents.

## 6.5 CONCOMITANT THERAPY

For this protocol, a prescription medication is defined as a medication that can be prescribed only by a properly authorized/licensed clinician. Medications to be recorded in the source document are concomitant prescription medications, over-the-counter medications, supplements, and relevant treatments and/or procedures (e.g., lid scrubs, tea tree oil, etc.). All concomitant medications including over-the-counter medications and nutritional supplements used within the 30 days prior to the first visit will be documented. Any changes to concomitant medication use or initiation of new medications will be reported throughout the study.

For the duration of the study, any therapy considered necessary for the participant's welfare may be given to the participant at the discretion of the investigator. Initiation of new medications or changes to concomitant medications should be recorded in the source document.

### 6.5.1 RESCUE MEDICINE

No rescue medication is available for this indication.

## 7 STUDY TREATMENT DISCONTINUATION AND PARTICIPANT DISCONTINUATION

### 7.1 DISCONTINUATION OF STUDY TREATMENT

Discontinuation from use of the study treatment does not mean discontinuation from the study, and remaining study procedures should be completed as indicated by the study protocol. If a clinically significant finding is identified after enrollment, the investigator or qualified designee will determine if any change in participant management is needed. Any new clinically relevant finding will be reported as an AE. Participants to be discontinued for AE(s) will be followed until the event is resolved or considered medically stable by the investigator.

The data to be collected at the time of study treatment discontinuation may include the following:

- An AE assessment and performance of safety assessments including visual acuity, IOP, slit lamp biomicroscopy, endothelial cell density, hematology, blood chemistry, drug concentration analysis and urinalysis
- Any follow-up evaluations required per investigator determination

Temporary discontinuation of the study treatment could include the onset of such conditions as an allergic conjunctivitis or signs or symptoms of eyelid allergy (e.g., injection, swelling, itching, etc.). Per investigator discretion, the study treatment could be discontinued until such a time that the allergic

conjunctivitis has shown sufficient improvement such that the study treatment could be re-started. Re-challenging with the study treatment could help to determine if the allergic response is related to the study drug.

The principal investigator reserves the right to discontinue the study at his/her site for any safety, ethical or administrative reason at any time.

## 7.2 PARTICIPANT DISCONTINUATION FROM THE STUDY

Participants are free to discontinue from participation in the study at any time upon request. An investigator may discontinue a participant from the study for the following reasons:

- Pregnancy
- If any clinical AE or other medical condition or situation occurs such that continued participation in the study would not be in the best interest of the participant
- If the participant meets an exclusion criterion (either newly developed or not previously recognized) that precludes further study participation
- Reasons relating to COVID-19
- Other (specify reason)

The reason for participant discontinuation from the study will be recorded on the exit eCRF. Participants who sign the informed consent form and are randomized but do not receive the study treatment will not be replaced. Participants who sign the informed consent form, are randomized and receive the study treatment and subsequently discontinue, or are discontinued from the study, will not be replaced.

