## 5.5 STRATEGIES FOR RECRUITMENT AND RETENTION

It is anticipated that at least 500 patients will be screened in order to reach target enrollment. The source of participants is expected to come primarily from outpatient clinics and the general public. As *Demodex* positive patients are widely available, participants are expected to come from in-office visits of participating investigators. In the general public, participants may be identified by their symptoms (e.g., itching and burning of the lids margins) and can be reached through print advertisements (e.g., newspaper, magazine advertisement, flyer, poster, etc.); social media; radio or television advertisement; and/or telephone screening script.

As the risk to participants is considered minimal, employees of the study site and family members of site staff may be invited to participate in the clinical trial. Site staff who work on the clinical trial are not eligible to participate.

To retain participants, participants may receive visit reminders and some reimbursement for their time and travel expenses.

In the event prohibited medications / treatments are indicated for care, participants will not be discontinued.

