The reasons for premature study discontinuation will be summarized by treatment arm for all discontinued subjects. Percentages will be calculated using randomized subjects as the denominator. The reasons for study discontinuation that will be summarized include pregnancy, significant study treatment non-compliance per PI determination, exclusion criterion, reasons relating to COVID-19, AE, and other. Withdrawal due to lack of efficacy will be summarized by treatment arm. A subject listing will be provided that includes the date of and reason for premature study discontinuation.

The number and percentage of subjects with any deviation, major deviation, minor deviation, and the total number of deviations related to COVID-19 will be summarized by treatment arm for all randomized subjects. The protocol deviations that will be summarized include the following categories: informed consent, inclusion/exclusion and randomization, test article/study drug instillation and assignment at site, improper protocol procedures at site, site's failure to report SAE/AE, visit out of window (missed, early, or late), subject non-compliance with test article, subject's use of prohibited concomitant medication, subject's failure to follow instructions, other, COVID-19: visit missed, COVID-19: assessment not performed, and COVID-19: other. A subject listing will be provided that includes the date of the deviation, the deviation code, the deviation description, classification of whether the deviation was judged to be COVID-19 related,

and the classifications of whether the deviations were judged to be major or minor and potential impact on the primary efficacy endpoint based on a masked review.

In addition, subject listings will be provided that include informed consent date, inclusion and exclusion criteria violations, and exclusions from any population, subjects affected by COVID-19, and withdrawal due to lack of efficacy. Details of the study randomization, including randomization date, site, randomized treatment, and actual treatment, will also be included within a subject listing.

Tables and listings for subject disposition and protocol deviations will be generated after the conclusion of Milestone 1 and will be re-run after the conclusion of Milestone 2, as described in [Section 2.7](#).

10. Demographic and Pretreatment Variables

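### Protocol 7.2 lets an investigator end study participation for an exclusion criterion or, through its open category, for non-compliance, so a Day 43 outcome that might have been collected can be imputed instead

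*Protocol*

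**What the plan says.** - **Protocol 7.2** lists reasons for which an investigator *may* discontinue a participant from the study. One is: "If the participant meets an exclusion criterion (either newly developed or not previously recognized) that precludes further study participation". Another is an open category, "Other (specify reason"). Non-compliance is not named.
- **SAP Section 9** lists the reasons for study discontinuation to be tabulated. They include "significant study treatment non-compliance per PI determination, exclusion criterion", and adverse event is a separate entry.
- **Protocol 9.4.2 (Missing Data), SAP 2.6 and SAP 13.1** count data missing after withdrawal for lack of efficacy or an adverse event as failure. Data missing after withdrawal for any other reason are multiply imputed by randomised arm, under missing at random. Stopping the drug and non-optimal compliance are ignored under a treatment-policy strategy.
- **Protocol 7.1** separates stopping treatment from leaving the study and says that "remaining study procedures should be completed as indicated by the study protocol".
- **Protocol 5.5**: "In the event prohibited medications / treatments are indicated for care, participants will not be discontinued".
- **Protocol 6.4**, on dosing: "Participants will be reinstructed on dosing compliance and this will be documented in the source documents".

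**The concern.** A treatment-policy strategy for non-compliance does its work only if the Day 43 outcome is observed. A participant who doses poorly and stays contributes a real collarette grade. One whom the investigator removes for the same behaviour contributes an imputed grade, drawn from a model fitted to the same arm. If those removed would have done worse than others in their arm, the imputed values are too favourable, more so in the TP-03 arm, where the cure rate is higher. What is at stake is a small bias in the estimated difference, and the loss of data that a visit already on the schedule could have supplied.

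**Working it through.** **1. Where the route is open**

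| Event | Text that applies | Day 43 if the participant exits early |
|---|---|---|
| New infection, inflammation or hypersensitivity | Protocol 7.1: "Any new clinically relevant finding will be reported as an AE" | Failure, if recorded as an adverse-event withdrawal |
| Prohibited treatment indicated for care | Protocol 5.5: no discontinuation | Observed |
| Ineligibility found late, concurrent trial enrolment, or lid products or cosmetic lash procedures used by choice | Protocol 7.2 exclusion-criterion reason | Same-arm imputation |
| Poor dosing compliance | Protocol 6.4 reinstruction; exit only through the open category, as SAP 9 anticipates | Same-arm imputation |

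The last two rows are the gap. The data that Protocol 7.1 says may be collected when treatment stops are safety assessments and "Any follow-up evaluations required per investigator determination". SAP 3.1 leaves assessments at unscheduled visits largely to discretion. Neither requires a collarette grade, and the SAP 3.2 schedule shows no early-exit visit.

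**2. The plan's own figure**

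Inputs (Protocol 9.2, SAP 5): 150 per arm, one-sided 0.025, pooled two-proportion test. Power is Φ[(difference − 1.96·SE₀)/SE₁], with SE₀ pooled and SE₁ unpooled.

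- 80.0% vs 15.8%: (0.642 − 0.113)/0.0442 = 12.0, so power is above 99.99%.
- 44.0% vs 7.4%: (0.366 − 0.099)/0.0458 = 5.8, so power is above 99.99%.

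Both agree with the stated approximately 99% and greater than 99%.

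**3. Size of the overstatement**

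Assumptions, none of them from the documents: a share w of an arm exits, w is 2% or 5% (about 4 or 10 of 209), and all who exit would have failed. Saturn-1 rates (44.0% and 7.4%) are taken as the true whole-arm rates.

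Completers then have a cure rate of p/(1 − w). If imputation fills the exits at that rate, the arm is overstated by p·w/(1 − w).

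| Exits in | Formula | w = 2% | w = 5% |
|---|---|---|---|
| Both arms equally | 0.366·w/(1 − w) | 0.75 points | 1.93 points |
| TP-03 only | 0.440·w/(1 − w) | 0.90 points | 2.32 points |
| Vehicle only | −0.074·w/(1 − w) | −0.15 points | −0.39 points |

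If the Saturn-1 rates are instead read as completers' rates, equal exits give 0.366·w = 0.73 and 1.83 points. For equal exits the range is therefore about 0.7 to 1.9 points.

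These are worst cases for the assumed w. The SAP 13.1 model uses baseline and Days 8, 15 and 22, so a participant who exits with poor earlier grades is imputed less favourably than the arm average. The reduction is small for an exit before Day 8, when only baseline is available.

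**4. Comparison with sampling error and power**

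- Standard error of the difference at 209 per arm: √[(0.440·0.560 + 0.074·0.926)/209] = 3.88 points.
- Power at 150 per arm with 5% of each arm counted as failure (41.8% vs 7.03%): (0.348 − 0.097)/0.0454 = 5.5, so power is still above 99.99%.

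**5. What the 2% repeat in SAP 2.6 covers**

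This repeat counts data missing because of treatment discontinuation or non-compliance as failures. It applies to the primary analysis only and does not reach exclusion-criterion exits. The denominator is not stated. On 418 randomised, 2% is 8.36, so nine missing values trigger it. With eight exits and no repeat, the worst case is 0.366·4/205 = 0.71 points if split evenly, or 0.440·8/201 = 1.75 points if all are in TP-03.

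**The case against.** The strongest reply is that little remains once the surrounding text is read, and much of that reply stands.

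- The exclusion-criterion reason applies only where the criterion precludes further participation, so the lost outcome may not always have been obtainable. This stands, and is why the point says *might*.
- Non-compliance as a ground for exit is an inference. SAP 9 is a reporting list and authorises nothing, and the visible instruction in Protocol 6.4 is to reinstruct. Text is redacted in 6.4 immediately before that instruction, where a compliance rule could sit. This also stands. Still, the SAP expects such exits to be reported.
- A reader might infer that imputing these participants breaches the full analysis set. It does not: imputation keeps every randomised participant in the analysis as randomised.
- A reader might infer that imputing exclusion-criterion exits departs from the estimand. It does not: SAP 2.6 declares the hypothetical strategy with same-arm imputation for other withdrawals. The conflict is confined to non-compliance exits.
- The sponsor has planned Sensitivity I (imputation from vehicle), Sensitivity V (all missing as failure), the 2% repeat, and all-missing-as-failure analyses for the secondary endpoints. These show how far the result moves under other assumptions, and no further analysis is needed. They cannot recover the outcome itself.

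**Conclusion.** The point holds as a low-priority, cheap improvement. Protocol 7.2 permits an exit that can replace a Day 43 outcome with same-arm imputation. For non-compliance this conflicts with the treatment-policy strategy in SAP 2.6 and the principle in Protocol 7.1. For an exclusion criterion it loses information without contradicting the plan.

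Under the assumptions of 2% to 5% exits in each arm, all of them failures, and Saturn-1 rates, the overstatement is at most about 0.7 to 1.9 points, under half of one standard error. It reverses in sign if only vehicle participants exit.

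Two stronger readings are not supported. The protocol does not require removal of non-compliant or ineligible participants. Nor is the primary conclusion at risk. The 30% discontinuation allowance in Protocol 9.2 is not evidence of a high exit rate by this route, because the text ties the enlarged enrolment to COVID-19 and possible site closures.

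Confidence is medium: several exclusion criteria, part of Protocol 6.4 and the protocol's own visit schedule are not visible.

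**What to change.** In Protocol 7.2, replace the exclusion-criterion reason and qualify the open category, so that the new text does not sit beside a reason that contradicts it. Suggested wording:

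> Meeting an exclusion criterion after randomisation, discovering one that was present earlier, or not complying with dosing may lead to stopping study treatment. None of these, alone or under the open category, is a reason to end study participation. The participant is asked to attend Day 43 for collarette, erythema and *Demodex* assessments, unless consent is withdrawn or continuing is not in the participant's best interest.

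Leave the pregnancy, adverse-event or best-interest, COVID-19 and voluntary exits unchanged. The SAP needs no change: its Section 9 categories will report by arm any such exits that still occur.

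The cost is an IRB review and a few Day 43 visits for participants off treatment. Some will decline, and the best-interest exception still leaves room for judgement, so the change reduces the loss without removing it.

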## 7.3 LOST TO FOLLOW-UP

A participant will be considered lost to follow-up if he or she fails to return for their scheduled visit within the visit window and is unable to be contacted by the study site staff.

The following actions must be taken if a participant fails to return to the clinic for a required study visit:

- The site will attempt to contact the participant and reschedule the missed visit as soon as possible, counseling the participant on the importance of continuing the administration of the study drop and of maintaining the assigned visit schedule. In addition, the site should ascertain if the participant wishes to and/or should continue in the study.
- Before a participant is deemed lost to follow-up, the investigator or designee will make every effort to regain contact with the participant (where possible, three telephone calls and, if necessary, a certified letter to the participant's last known mailing address or local equivalent methods). These contact attempts should be documented in the participant's medical record or study file.
- Should the participant continue to be unreachable, he or she will be considered to have discontinued from the study with a primary reason of lost to follow-up.

## 8 STUDY ASSESSMENTS AND PROCEDURES

### 8.1 EFFICACY ASSESSMENTS

The efficacy assessments performed include the following:

- Assessment of collarette grade
- Eyelash epilation and mite counts
- Assessment of erythema grade

The procedures are described in detail in Appendix A. All procedures/evaluations will be performed by qualified personnel. In addition, mite counts will be performed by trained clinical or SMO staff.

## 8.2 SAFETY AND OTHER ASSESSMENTS

The safety and other assessments to be performed include the following:

- Adverse events
- Corrected distance visual acuity
- Slit lamp biomicroscopy assessment
- Corneal staining
- IOP measurement
- [REDACTED]
- [REDACTED]
- [REDACTED]
- [REDACTED]
- [REDACTED]

The procedures are described in detail in Appendix A. All procedures/evaluations will be performed by qualified personnel.

## 8.3 ADVERSE EVENTS AND SERIOUS ADVERSE EVENTS

### 8.3.1 DEFINITION OF ADVERSE EVENTS (AE)

Adverse event is defined as any untoward medical occurrence associated with the use of a drug in humans, whether or not considered drug-related (21 CFR 312.32 (a)).

### 8.3.2 DEFINITION OF SERIOUS ADVERSE EVENTS (SAE)

An AE or suspected adverse reaction is considered "serious" if, in the view of either the investigator or sponsor, it results in any of the following outcomes: death, a life-threatening AE, inpatient hospitalization or prolongation of existing hospitalization, a persistent or significant incapacity or substantial disruption of the ability to conduct normal life functions, or a congenital anomaly/birth defect. Important medical events that may not result in death, be life-threatening, or require hospitalization may be considered serious when, based upon appropriate medical judgment, they may jeopardize the participant and may require medical or surgical intervention to prevent one of the outcomes listed in this definition. Examples of such medical events include allergic bronchospasm requiring intensive treatment in an emergency room or at home, blood dyscrasias or convulsions that do not result in inpatient hospitalization, or the development of drug dependency or drug abuse. Serious

adverse events include drug deficiencies that might have led to an SAE if a) suitable action had not been taken or b) intervention had not been made or c) if circumstances had been less fortunate.

Events that are considered sight-threatening in the opinion of the investigator will be considered SAEs.

A planned hospitalization for a pre-existing condition without a serious deterioration in health is not considered to be an SAE. Hospitalization for less than 24 hours is not considered an SAE unless the precipitating event was unanticipated and also related to the investigational drug.

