#### 8.3.3.3 EXPECTEDNESS

The investigator will be responsible for determining whether an AE is expected or unexpected. An AE will be considered unexpected if the nature, severity, or frequency of the event is not consistent with the risk information previously described for the study treatment. Expectedness should be determined if the AE is characterized as related to treatment and is serious (met one or more of the criteria for an SAE).

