#### 8.3.4 TIME PERIOD AND FREQUENCY FOR EVENT ASSESSMENT AND FOLLOW-UP

The occurrence of an AE or SAE may come to the attention of study personnel during study visits and interviews of a study participant presenting for medical care, or upon review by a study monitor. At study visits, study personnel should pose general questions to the participant to ascertain if the participant experienced any issues prior to the visit.

All AEs, including local and systemic reactions not meeting the criteria for SAEs, will be captured on the appropriate eCRF. Information to be collected includes event description, date of onset, clinician's assessment of severity, relationship to study product (assessed only by those with the training and authority to make a diagnosis), and date of resolution/stabilization of the event. All AEs occurring while in the study must be documented appropriately regardless of relationship.

Any medical condition that is present at the time that the participant is screened will be considered as Baseline and not reported as an AE. However, if the study participant's condition deteriorates at any time during the study, it will be recorded as an AE.

Changes in the severity of an AE will be documented to allow an assessment of the duration of the event at each level of severity to be performed.

The investigator or designee will record all reportable events with start dates occurring any time after study drug is first administered until 7 (for non-serious AEs) or 30 days (for SAEs) after the last day of study participation. At each study visit, the investigator will inquire about the occurrence of AE/SAEs since the last visit. Events will be followed for outcome information until resolution or stabilization.

Whenever possible, recognized medical terms should be used when recording AEs. Colloquialisms and/or abbreviations should not be used. Only one medical concept, preferably a diagnosis instead of individual symptoms, should be recorded as the event (e.g., record congestive heart failure rather than dyspnea, rales and cyanosis). However, if a constellation of signs and/or symptoms cannot be medically characterized as a single diagnosis or syndrome at the time of reporting, each individual sign or symptom should be recorded as a separate AE. A diagnosis that is subsequently established should be reported as follow-up information.

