### 8.3.6 SERIOUS ADVERSE EVENT REPORTING

The study clinician will immediately report to the sponsor and Medical Monitor any SAE, whether or not considered study treatment-related, including those listed in the protocol or investigator brochure and must include an assessment of whether there is a reasonable possibility that the study treatment caused the event [21 CFR 312.64(b)]. Serious adverse events must be reported immediately to the below listed individuals using the Serious Adverse Event Report (SAER) form. Sites will also be instructed to document the event in the Serious Adverse Event eCRF.

[REDACTED]	[REDACTED]

All SAEs will be followed until satisfactory resolution or until the site investigator deems the event to be chronic or the participant is stable. Other supporting documentation of the event may be requested by the study sponsor and should be provided as soon as possible.

The study sponsor or designee will be responsible for notifying the Food and Drug Administration (FDA) of any unexpected fatal or life-threatening suspected adverse reaction as soon as possible, but in no case later than 7 calendar days after the sponsor's initial receipt of the information [21 CFR 312.32(c)(2)]. In addition, the sponsor must notify the FDA and all participating investigators in an Investigational New Drug (IND) safety report of potential serious risks, from clinical trials or any other source, as soon as possible, but in no case later than 15 calendar days after the sponsor determines that the information qualifies for reporting [21 CFR 312.32(c)(1)]. In each IND safety report, the sponsor must identify all IND safety reports previously submitted to the FDA concerning a similar suspected adverse reaction and must analyze the significance of the suspected adverse reaction in light of previous, similar reports or any other relevant information. The sponsor must report any suspected adverse reaction that is both serious and unexpected. The sponsor must report an AE as a suspected adverse reaction only if there is evidence to suggest a causal relationship between the drug and the AE.

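### Under the hospitalization criterion, a stay of less than 24 hours is serious only if the event was unanticipated and drug-related, so causality decides seriousness for short admissions

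*Protocol*

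**What the plan says.** Protocol 8.3.2 classes an event as serious if, "in the view of either the investigator or sponsor, it results in any of the following outcomes", and the listed outcomes include "inpatient hospitalization or prolongation of existing hospitalization". At that point there is no lower limit on length of stay and no reference to cause. The section ends with two exclusions. The first covers admissions planned for a pre-existing condition that has not seriously worsened. The second is: "Hospitalization for less than 24 hours is not considered an SAE unless the precipitating event was unanticipated and also related to the investigational drug".

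Elsewhere the protocol keeps seriousness and causality apart:

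- 8.3.1 defines an AE as "any untoward medical occurrence associated with the use of a drug in humans, whether or not considered drug-related".
- 8.3.3.3 names them as two separate conditions: "Expectedness should be determined if the AE is characterized as related to treatment and is serious".
- 8.3.4 states: "All AEs occurring while in the study must be documented appropriately regardless of relationship".
- 8.3.6 requires immediate reporting to the sponsor and Medical Monitor of "any SAE, whether or not considered study treatment-related", with the causality assessment supplied as part of that report.

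The collection period depends on seriousness. Under 8.3.4, events are recorded "until 7 (for non-serious AEs) or 30 days (for SAEs) after the last day of study participation".

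**The concern.** Whether an event is serious should follow from what happened to the participant. Whether the drug caused it is a separate judgment, made in this protocol by the examining clinician (8.3.3.2). The 24-hour sentence joins the two. For a short admission, the clinician must settle causality before anyone knows whether an SAE report is due, although 8.3.6 treats causality as an item within the report.

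At stake are the speed with which the sponsor and Medical Monitor hear of short unplanned admissions, the completeness of the SAE summaries, and the length of time after last participation during which such events are collected. Safety is part of the primary objective (Protocol section 3), so the SAE outputs ought to rest on a definition that does not vary with individual causality calls.

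**Working it through.** No sample size, rate or error level enters this point. The check is a comparison of rules, plus one count of days.

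**Step 1: apply the closing sentence of 8.3.2.** Take an inpatient stay of less than 24 hours that meets no other seriousness criterion and is not an admission planned for a pre-existing condition. The general definition classes it as serious in every row below.

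| Event judged | Anticipated? | General outcome criterion | Closing sentence |
|---|---|---|---|
| Related | No | SAE | SAE |
| Related | Yes | SAE | Not an SAE |
| Not related | No | SAE | Not an SAE |
| Not related | Yes | SAE | Not an SAE |

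Two conditions must both hold, so relatedness is necessary but not sufficient. Comparing the first and third rows, the same unplanned stay changes class on the causality judgment alone.

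**Step 2: ask whether a definition of inpatient stay explains the rule.** A sponsor may wish to leave out emergency-room or observation stays. That would be a rule on duration or admission status, and it would give the same answer whatever the cause. It does not account for the relatedness condition. Planned admissions are already handled by the preceding sentence of 8.3.2.

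**Step 3: follow an unrelated, unplanned short admission through the documents.**

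- Reporting: immediate notification under 8.3.6 is replaced by timely eCRF entry under 8.3.5.
- Outputs: SAP 14.2 plans treatment-emergent SAEs in the overall summary, a separate treatment-emergent SAE summary and a separate SAE listing. The event appears in none of these. It does appear in the ocular or non-ocular TEAE tables and in the general AE listing.
- Collection: the period after last participation falls from 30 days to 7 days. Onset on days 8 to 30 falls outside it, a span of 30 − 7 = 23 days in which the event need not be recorded in any form.

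**Step 4: check 8.3.6 for a direct conflict.** Its reporting duty covers events already classed as SAEs, and 8.3.2 decides that class. Both can be followed literally. The direct inconsistency lies inside 8.3.2, between the unconditional hospitalization criterion and the closing sentence. The effect on 8.3.6 is that unrelated short stays are removed before its rule can apply to them.

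**The case against.** The case for leaving the text alone has several parts, and some of them limit the point.

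- *Other routes to seriousness stay open.* A reader might infer that no short stay can be an SAE unless it is drug-related. The documents do not support that. Death, life-threatening events, incapacity, important medical events and sight-threatening events all qualify under 8.3.2 with no causality test. The important medical events include examples that need no inpatient admission. The restriction applies only to the hospitalization criterion.
- *8.3.6 is not literally contradicted.* A reader might infer a flat contradiction. Step 4 of the working shows that the conflict there is one of effect.
- *The sponsor is not blind to these events.* A reader might infer that the sponsor cannot make its own assessment. Events within the AE window are entered on the eCRF with description, severity and relationship, and central oversight rests with the Medical Monitor (8.3.4, 10.1.5). Notification is slower, but it is not lost. Only events on days 8 to 30 after last participation can go unrecorded.
- *The bar for relatedness is low.* Under 8.3.3.2 the product is to be treated as suspect in every case. Potentially Related needs only a possible link, even where other explanations exist, and Not Related is for events with no plausible direct link. Many short stays with any suspicion attached would pass. This shrinks the affected group.
- *No signal failure or between-arm bias is shown.* A reader might infer that a rare systemic effect would first surface in these events, or that the SAE table is biased between arms. Nothing in the documents supports the first. As to the second, the same rule applies to both arms under masking, and the excluded events remain in the TEAE tables.

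What remains is the fault in the rule itself. None of these arguments explains why cause should alter the seriousness of an identical hospital stay.

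**Conclusion.** The point holds as a fault in the SAE definition. Under the hospitalization criterion of Protocol 8.3.2, a stay of less than 24 hours counts only if the event was both unanticipated and related, which does not fit the outcome-based definition in the same section. Followed as written, the rule moves unrelated short admissions out of immediate reporting and out of the SAE outputs, and shortens their collection period by 23 days.

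The size is modest. The documents state no expected rate of short admissions. That few will occur is an assumption, based on an outpatient eye-drop trial enrolling up to 418 participants. No efficacy endpoint, estimand or sample-size calculation is affected. The conclusion also assumes that sites apply the closing sentence as written and that no other seriousness criterion is met. The correction is worth making because it is cheap and the current rule serves no purpose that the documents state.

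**What to change.** Amend the closing sentence of Protocol 8.3.2 so that it agrees with the outcome-based definition above it and with 8.3.6. There are two ways to do this:

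1. Delete the condition that the event be related to the investigational drug. Unanticipated short admissions then count whatever their cause. Anticipated short stays would remain excluded, so the sponsor should confirm that this is intended and say what unanticipated means here.
2. If the aim is to keep stays that are not true inpatient admissions out of the SAE count, state a minimum-stay or admission-status definition of inpatient hospitalization and apply it identically to related and unrelated events.

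Either option costs a one-sentence amendment, a short notice to sites and a few more SAE forms. The SAP needs no change, because its SAE outputs take the classification from the protocol.
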